#### 11.3.1.2 Secondary Efficacy Analyses

For the best response and the response rate, frequency tables will be prepared, and the 95% CI will be calculated.

For OS, event-free survival, and leukemia-free survival, Kaplan-Meier curves will be prepared, and medial survival and the 95% CI will be calculated using the method of Brookmeyer and Crowley.

For the transplantation rate, frequency tables will be prepared, and the 95% CI will be calculated.

#### 11.3.1.3 Exploratory Efficacy Analyses

Not applicable

# 11.3.2 Pharmacokinetic/Pharmacodynamic Analyses

#### 11.3.2.1 Pharmacokinetic Analyses

In the pharmacokinetic analysis set, summary statistics of the plasma concentrations of quizartinib and AC886 will be calculated by dose at each time point, and plasma concentration-time profiles will be prepared. Summary statistics of pharmacokinetic parameters will be calculated by dose at each time point.

A population pharmacokinetic analysis of quizartinib and quizartinib exposure-response analysis will be performed to evaluate the relationship between the dose and exposure as well as between exposure and the efficacy or safety endpoints. If population pharmacokinetic and exposure-response analyses are performed, the reports should be prepared separately.

# 11.3.2.2 Pharmacodynamic Analyses

Not applicable

#### 11.3.2.3 Biomarker Analyses

In the biomarker analysis set, measured values of plasma inhibitory activity of quizartinib on phosphorylated FLT3 and c-Kit proteins will be summarized at each time point.

#### 11.3.2.4 Pharmacogenomic Analyses

Not applicable

#### 11.3.3 Safety Analyses

Safety analyses will be performed in the safety analysis set.

AEs that occur or worsen relative to the pre-treatment state after the first dose of the study drug (treatment emergent AEs [TEAEs]) will be tabulated. AEs will be coded using the Medical Dictionary for Regulatory Activities (MedDRA) terminology developed by the ICH, and be tabulated by body organ group using the MedDRA system organ class (SOC) and by AE term using preferred terms (PTs).

### 11.3.3.1 Adverse Event Analyses

For TEAEs and TEAEs assessed as "related" to the study drug, frequency tables will be prepared as classified below. The grade of each AE will be assessed according to the CTCAE v4.0 Japanese version. In the tabulation by grade, only the highest-grade event in each patient will be included.

- TEAEs (by grade; including classification into Grade 3 or more severe events)
- Serious TEAEs
- Patients who have interrupted treatment with the study drug due to TEAEs
- Patients with treatment discontinuation because of TEAE

For TEAEs and TEAEs assessed as "related" to the study drug, frequency tables will be prepared by event as classified below. The grade of each AE will be assessed according to the CTCAE v4.0 Japanese version. If a patient reports the same event several times, only the highest-grade event will be counted for tabulation.

- TEAEs
- TEAEs by grade (including classification into Grade 2 or less severe events and Grade 3 or more severe events)
- Serious TEAEs
- TEAEs leading to interruption of treatment with the study drug
- TEAEs causing treatment discontinuation

# 11.3.3.2 Clinical Laboratory Evaluation Analyses

For hematology and blood chemistry tests, summary statistics of measured values and changes from baseline will be calculated at each time point. For urinalysis (except

specific gravity), shift tables of measured values at baseline and those at each time point will be prepared. For specific gravity, summary statistics will be calculated at each time point.

The number and proportion of patients who meet the criteria specified in the Food and Drug Administration (FDA) Guidance for Industry Drug-induced Liver Injury (DILI) in terms of ALT, AST, total bilirubin, and ALP will be calculated, and evaluation of drug-induced serious hepatotoxicity (eDISH) plots will be prepared.

# 11.3.3.3 Vital Sign Analyses

For blood pressure (systolic and diastolic), pulse rate, body temperature, and body weight, summary statistics of measured values and changes from baseline will be calculated at each time point.

#### 11.3.3.4 Electrocardiogram Analyses

For 12-lead ECG findings, shift tables of normal-abnormal assessments at baseline and each time point will be prepared. For PR, QRS, RR, QT, QTcB, and QTcF intervals and heart rate, summary statistics of measured values and changes from baseline will be calculated at each time point. For QTcF, frequency tables will also be prepared according to the following categories.

#### Absolute QTcF:

- QTcF > 450 ms
- QTcF > 480 ms
- QTcF > 500 ms

Changes in QTcF from baseline:

- Increase in QTcF from baseline > 30 ms
- Increase in QTcF from baseline > 60 ms

#### 11.3.3.5 Analyses of Physical Findings

Not applicable

# 11.3.3.6 Exploratory Safety Analyses

Not applicable

#### 11.3.4 Other Analyses

Not applicable

#### 11.3.5 Blinded Review

Not applicable

#### 11.4 Interim Analysis

This study is planned with a two-stage design; in Stage 1, interim analysis will be performed when 25 patients are included in the efficacy analysis set. If it is decided to continue the study based on the interim analysis (for the assessment criteria, see "11.4.3 Criteria"), registration of patients will be continued until 41 patients are included in the efficacy analysis set (16 patients in Stage 2). Registration of patients will be continued during the course of the interim analysis.

#### 11.4.1 Purposes of the Interim Analysis

In this study, interim analysis that includes early termination of the study due to efficacy and futility is planned for the following reasons. In the interim analysis, the secondary efficacy endpoints, safety, pharmacokinetics, and biomarkers will be evaluated in addition to the primary endpoint, CRc rate.

Since the sample size of this study is calculated based on the alternative hypothesis that the CRc rate is 42%, which is the lower limit of the CRc rate of 42% to 47% obtained in overseas Phase 2 studies of AC220 monotherapy in patients with FLT3-ITD positive relapsed or refractory AML (Studies AC220-002 and 2689-CL-2004) (see Section 11.5), the true CRc rate with quizartinib in this study may be higher than 42%. In such a case, to allow early completion of this study, interim analysis including early termination due to efficacy is planned. In addition, since the results of overall Phase 2 studies are highly uncertain due to a limited number of patients, taking the possibility that the true CRc rate with quizartinib may be about 23.5%, which is set as the threshold level into consideration, early termination due to futility is also included in the requirements for interim analysis.

#### 11.4.2 Possible Options to Be Taken at Interim Analysis

The following decisions will be made at the interim analysis. If it is decided to terminate the study early, the registration of patients will be discontinued; however, treatment with the study drug in patients who continue receiving the study drug will be continued until "5.7.1 Discontinuation Criteria for Treatment with the Study Drug" are met.

- Continuation of the study
- Early termination of the study due to efficacy
- Early termination of the study due to futility

#### 11.4.3 Criteria

The assessment criteria in Stage 1 (25 patients will be chosen from the efficacy analysis set in the order of registration) and at the end of Stage 2 (41 patients will be chosen from the efficacy analysis set in the order of registration) are shown below. Concerning patients for whom the study is continued as of the data cut-off date (see below) of the interim analysis, the best response will be calculated from the data collected up to the data cut-off date, and whether CRc is achieved or not will be assessed.

#### <Stage 1>

- The study will be continued if CRc is achieved in 4 to 10 patients.
- The study will be early terminated due to efficacy if CRc is achieved in 11 or more patients.
- The study will be early terminated due to futility if CRc is achieved in 3 or fewer patients.

# <Stage 2>

• Treatment will be determined to be effective (rejection of the null hypothesis) if CRc is achieved in 15 or more patients.

#### Data cut-off date:

The day when the best response is assessed as CR, CRp, or CRi, the day when treatment with the study drug is discontinued, or Day 1 of Cycle 4, whichever comes first, will be calculated for each patient. The latest day in the 25 patients included in the interim analysis is regarded as the data cut-off date. The above procedure will also apply to analysis at the end of Stage 2.

# 11.4.4 Data Monitoring Committee

An in-house Data Monitoring Committee, which consists of medical monitors, persons in charge of clinical procedures, biostatisticians, persons in charge of pharmacokinetic analysis, and persons in charge of modeling & simulation, will be established and will have responsibility to review the interim analysis results. In principle, the Data Monitoring Committee is supposed to make a decision on early termination of the study in accordance with "11.4.3 Criteria." However, continuation of the study may be

decided depending on the results of safety assessment of the interim analysis. In the review process, the Data Monitoring Committee might consult with external hematology oncology specialists as necessary. The review content and final decision on interim analysis will be recorded in the meeting minutes.

# 11.5 Determination of Sample Size

The remission induction rate is remarkably low in patients with relapsed or refractory AML, compared with anticancer therapy introduced in patients with newly diagnosed AML, and it is as low as 12.8% (76/596) according to the report by Giles et al. The results of FLT3-ITD-positive AML patients have also been reported by Ravandi and Levis 18) as follows: The rate of remission induction with salvage therapy was 23.5% (8/34) in patients with first relapsed AML, and the rate of remission induction was 11.3% (6/53) in the subgroup of patients who had a poor prognosis defined as initial remission sustained for 6 months or shorter after the initial treatment. In this way, considering that the remission induction rate in patients with relapsed or refractory AML varies among the reports and that the data of CRi, which is one of the elements comprising CRc, are not available in some reports, the threshold of the CRc rate in this study was set at 23.5% as the most conservative value among the values that are available for reference. Meanwhile, in preceding overseas Phase 2 studies of quizartinib monotherapy in patients with FLT3-ITD-positive relapsed or refractory AML (Studies AC220-002 and 2689-CL-2004), the CRc rate has been reported to be 42% to 47% at several doses of quizartinib including 30 mg and 60 mg. The expected CRc rate with quizartinib in this study was therefore assumed to be 42%.

The design shown in Table 11.5-1 was established to satisfy the following conditions, with a one-sided 5% significance level and 80% power, in reference to the optimal two-stage design under the alternative hypothesis proposed by Mander and Thompson.

- The number of patients evaluated in Stage 1 is approximately 25 (to assure a certain amount of safety information even if the study is early terminated in Stage 1).
- If the study is early terminated due to futility, the observed CRc rate is 12% or less (less than the lower limit of the remission induction rate reported).
- The probability of early termination due to efficacy under the condition of the expected CRc rate (42%) is approximately 50%.

Table 11.5-1 Number of Patients Evaluated at Each Stage and Assessment Criteria

	This Study	Mander*1
No. of patients assessed in Stage 1	25	19
Criteria for discontinuation due to futility in Stage 1	≤ 3	≤ 4
Criteria for discontinuation due to efficacy in Stage 1	≥ 11	≥9
No. of patients assessed at the end of Stage 2	41	41
Assessment criteria for efficacy at the end of Stage 2	≥ 15	≥ 15
Expected No. of patients under the alternative hypothesis	33.0	31.1

\*1 Optimal two stage design under the alternative hypothesis proposed by Mander and Thompson

Based on the above, registration of patients will be continued until 25 patients assessable for efficacy are enrolled in Stage 1 and 16 patients assessable for efficacy are enrolled in Stage 2.

Shown below are the operating characteristics when the two-stage design applies to this study.

CRc Rate (True Value)	Probability of Discontinuation Due to Futility (Stage 1)	Probability of Discontinuation Due to Efficacy (Stage 1)	Probability of Assessment as Futility (Entire Study)	Probability of Assessment as Efficacy (Entire Study)
23.5%	0.128	0.019	0.952	0.048
42.0%	0.001	0.496	0.186	0.814

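### Should the Stage 1 futility bound of 3 of 25 change, given that Section 11.5 also reports a remission rate of 11.3% and the bound seldom stops at 23.5%?

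*Combined protocol and SAP*

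**What the plan says.** Section 11.5 of the protocol builds a two-stage design (25 patients, then 16 more) at a one-sided 5% level with 80% power. The threshold CRc rate is 23.5% and the expected rate is 42%. One of three listed conditions is that, at a futility stop, "the observed CRc rate is 12% or less (less than the lower limit of the remission induction rate reported".

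The opening paragraph of the section gives three historical rates:

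- For relapsed or refractory AML in general, "it is as low as 12.8% (76/596".
- For FLT3-ITD-positive first relapse, 23.5% (8/34).
- For FLT3-ITD-positive patients whose first remission was short, "the rate of remission induction was 11.3% (6/53) in the subgroup of patients who had a poor prognosis".

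Section 11.4.1 explains why a futility stop is included: "the true CRc rate with quizartinib may be about 23.5%, which is set as the threshold level into consideration". The operating-characteristics table in Section 11.5 has a column headed "Probability of Discontinuation Due to Futility (Stage 1", with 0.128 at 23.5% and 0.001 at 42%. Table 11.5-1 sets the chosen bound (3 or fewer of 25) beside that of the reference optimal design (4 or fewer of 19) and compares the two on "Expected No. of patients under the alternative hypothesis": 33.0 against 31.1.

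The bound of 3 or fewer is the same in the Synopsis, Section 3.1, Section 11.4.3 and Table 11.5-1.

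**The concern.** Two things look wrong.

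First, 12.0% is not below every reported rate. It is below 12.8% and above 11.3%. The 11.3% subgroup also resembles the early-relapse patients admitted by inclusion criterion 4. A reader could conclude that the stopping bound rests on a comparison its own section contradicts, and that a literal reading would require 2 or fewer of 25.

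Second, the futility rule is motivated by a true rate near 23.5%, yet at that rate it fires about one time in eight. Studies with 4 or 5 responders in 25 go on although they then need 11 or 10 responders in 16 patients. Up to 16 further patients could be treated with a drug no better than the threshold, in a study that almost cannot succeed. Raising the bound seems to cost almost no power.

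**Working it through.** **Inputs** (Sections 11.4.3 and 11.5): n1 = 25, N = 41, efficacy stop at 11 or more, final success at 15 or more, futility bound f = 3, rates 23.5% and 42%.

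**Formulas** (exact binomial, X1 = Stage 1 responders, X2 = responders among the 16 Stage 2 patients):

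- P(futility stop) = P(X1 ≤ f)
- P(success) = P(X1 ≥ 11) + Σ over x = f+1 to 10 of P(X1 = x) × P(X2 ≥ 15 − x)
- E[N] = 25 + 16 × P(continue)

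**The plan's own figures, f = 3**

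- At 23.5%: futility stop 0.1280, efficacy stop 0.0190, success 0.0482. E[N] = 25 + 16 × (1 − 0.1280 − 0.0190) = 38.6.
- At 42%: futility stop 0.0013, efficacy stop 0.4956, success 0.8137. E[N] = 25 + 16 × (1 − 0.0013 − 0.4956) = 33.0.

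Every printed value is reproduced. The reference design's 31.1 is reproduced as well.

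**The historical comparison**

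3/25 = 12.0%, 76/596 = 12.8%, 8/34 = 23.5% and 6/53 = 11.3%. The bracketed remark holds against the first two reported rates and misses the third by 0.7 points. The condition itself, 12% or less, is met exactly. A bound of 2 (2/25 = 8.0%) would satisfy the remark literally, but it would cut the stop probability at 23.5% to 0.046, the opposite of what the second worry asks for.

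**Other bounds, all else unchanged**

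| | f = 3 | f = 4 | f = 5 |
|---|---|---|---|
| Observed rate at the bound | 12% | 16% | 20% |
| Futility stop at 23.5% | 0.128 | 0.267 | 0.446 |
| Alpha | 0.0482 | 0.0482 | 0.0480 |
| E[N] at 23.5% | 38.6 | 36.4 | 33.6 |
| Futility stop at 30% | 3.3% | 9.0% | 19.3% |
| Futility stop at 35% | 1.0% | 3.2% | 8.3% |
| Futility stop at 42% | 0.1% | 0.6% | 1.8% |
| Power at 42% | 0.8137 | 0.8136 | 0.8126 |
| E[N] at 42% | 33.0 | 33.0 | 32.8 |

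**What f = 5 would save**

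At 23.5%, P(X1 = 4 or 5) = 0.3185, so the mean saving is at most 0.3185 × 16 = 5.1 patients. At 42% it is 33.05 − 32.78 = 0.3.

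The full saving will not be realised. Section 11.4 states that "Registration of patients will be continued during the course of the interim analysis". Each patient's contributing date can be as late as Day 1 of Cycle 4, and "The latest day in the 25 patients included in the interim analysis is regarded as the data cut-off date". If k Stage 2 patients are already registered when the decision is made, the saving is 0.3185 × (16 − k): 3.8, 2.5 and 1.3 for k = 4, 8 and 12. The values of k are assumptions, because no accrual rate is given.

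**Chance of final success after continuing**

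| Stage 1 result | at 23.5% | at 42% | at 47% |
|---|---|---|---|
| 4 of 25 | 0.02% | 2.8% | 6.7% |
| 5 of 25 | 0.1% | 8.0% | 16.1% |

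**The case for a change.** The strongest case for a change is that bound 5 is nearly free on the plan's formal criteria. Alpha stays below 5%, power stays above 80%, and the chance of an early efficacy stop at 42% stays at 0.496. Overall success falls by at most 0.13 points at true rates of 30%, 35% and 42%, because the extra stopped studies would nearly all have failed. The reference design stops with probability 0.527 at 23.5%, so much of that protection was given up in the move to 25 patients, and the text does not discuss the loss.

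All of this is arithmetically right, and the efficiency point stands as an observation. It does not show an error, for four reasons.

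- Section 11.4.1 names 23.5% as a possibility to allow for and sets no minimum stop probability there. The 0.128 is printed, and Table 11.5-1 shows the departure from the reference bound.
- The reference design is optimal under the alternative. On that criterion bound 5 gains 0.3 patients.
- Section 3.1 attaches a conclusion of ineffectiveness to a futility stop. Bound 5 would apply it at an observed 20%, above both 11.3% and 12.8%, and would discard the 12% condition. Bound 4 (16%) discards it too. At a true 30%, above the threshold, bound 5 adds 16.0 points of futility stops. Those studies would end with about 25 patients instead of 41 for CRc estimation and for the secondary efficacy, safety and pharmacokinetic objectives.
- Bound 5 can be justified by a rule that stops when the chance of final success at 42% is below 10%, but that cut-off has no source in the protocol. Section 11.4.1 treats 42% as the low end of 42% to 47%; at 47% the chance from 5 of 25 is 16.1%, and the same rule would continue.

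**Conclusion.** No change to the plan follows. The bracketed remark is a clerical slip: it is true of 12.8% and 23.5% and untrue of 11.3%. Analysts will apply the count of 3 or fewer, which is stated consistently and meets the 12% condition, so no decision, error rate or conclusion moves.

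The choice of 3 rather than 4 or 5 is a fair trade-off that the protocol discloses. The design delivers alpha 0.048 and power 0.814 against targets of 5% and 80%. A higher bound would save at most 5.1 patients on average at 23.5%, and 1.3 to 3.8 if 12 to 4 Stage 2 patients are already registered. Against that stand more futility stops at intermediate rates and less secondary, safety and pharmacokinetic information.

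These figures assume independent responses with a common rate and exactly 25 and 41 evaluable patients. The registration scenarios are illustrative.

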#### 11.6 Statistical Analysis Process

In this study, statistical analyses will be performed by a contract research organization (CRO) using SAS® Version 9.2 or a later version (SAS Institute Inc.) and WinNonliln (Version 6.0 or a later version). The detailed methods of statistical analyses will be specified in the separately prepared statistical analysis plan (SAP). To maintain the integrity of conclusions drawn from the statistical analyses and the study, the SAP should be fixed before database lock. If modifications to the SAP lead to a change in major contents of the protocol, the protocol will be amended. In the event of any deviation from the protocol-specified statistical analyses, the details will be described in the SAP.

#### 12. DATA INTEGRITY AND QUALITY ASSURANCE

The head of the study center and the investigator will provide direct access to all study-related documents, including source documents, at the implementation of monitoring and auditing by the sponsor as well as inspections by the regulatory authorities and the IRB. The sponsor will have direct access to all study-related documents, including source documents, at the study center when performing monitoring

and auditing to ensure appropriate implementation of the study and the reliability of the data. The sponsor will confer with the investigator in advance regarding the procedures for source document verification.

#### 12.1 Monitoring and Inspections

The sponsor, monitor of Mediscience Planning Inc. (MPI), and regulatory authority inspectors are responsible for contacting and visiting the investigator for the purpose of inspecting the facilities and, upon request, inspecting the various records of the study (eg, CRFs, source data, and other pertinent documents).

The verification of adherence to the protocol; completeness, accuracy, and consistency of the data; and adherence to ICH GCP and local regulations on the conduct of clinical research will be accomplished through a combination of onsite visits by the monitor and review of study data remotely. The frequency of the monitoring visit will vary based on the activity at each study center. The monitor is responsible for inspecting the CRFs and ensuring completeness of the study essential documents. The monitor should have access to subject medical records and other study related records needed to verify the entries on the CRFs. Detailed information is provided in the monitoring plan. The monitor will communicate deviations from the protocol, SOPs, GCP and applicable regulations to the investigator and will ensure that appropriate action(s) designed to prevent recurrence of the detected deviations is taken and documented.

The investigator agrees to cooperate with the monitor to ensure that any problems detected in the course of these monitoring visits are addressed to the satisfaction of the sponsor and documented.

In accordance with ICH GCP and the sponsor's audit plans, this study may be selected for audit by representatives from the sponsor. Audit of study center facilities (eg, pharmacy, drug storage areas, laboratories) and review of study related records will occur in order to evaluate the study conduct and compliance with the protocol, ICH GCP, and applicable regulatory requirements. The investigator should respond to audit findings. In the event that a regulatory authority informs the investigator that it intends to conduct an inspection, the sponsor shall be notified immediately.

#### 12.2 Data Collection

# 12.2.1 Completion of the Case Report Forms

The investigator, subinvestigator, or study staff will enter the data in the CRF in accordance with the CRF Completion Guideline that are provided by the sponsor.

CRF completion should be kept current to enable the monitor to review the subject's status throughout the course of the study. The CRF will be completed, reviewed, and signed off or e-signed by the investigator.

If the study employs paper CRFs, the investigator will sign and date the indicated places on the CRF. These signatures will indicate that the investigator inspected or reviewed the data on the CRF and the data queries, and agrees with the content.

If the study employs electronic data capturing (EDC), the investigator e-signs according to the study data flow.

Any clinical data entered in the CRF will be subjected to these data management procedures and will be included in the final study datasets according to Clinical Data Interchange Standards Consortium (CDISC) standards.

Daiichi Sankyo or MPI will supply electric case report forms (eCRFs). Daiichi Sankyo or MPI must complete eCRFs for each of subjects who have signed the ICF for the FLT3-ITD test as well as subjects who have signed the ICF for participation in the study and have undergone the screening test. If a subject is not treated, the reason must be recorded on the eCRF. All data collected during the study will be recorded in this individual, subject-specific eCRF. Instructions will be provided for the completion of the eCRF and any corrections made will be automatically documented via the EDC software's audit trail.

